3.0 PROTOCOL

3.1 Study Objectives

The primary objectives of this study are to evaluate the safety and effectiveness of the CellFX System in adults with low-risk basal cell carcinoma. Table 1 below reflects the study endpoints associated with the two objectives.

Table 1. Study Objectives and Endpoints

Objectives	Endpoints
Safety To evaluate the safety of the CellFX System in adults with low-risk basal cell carcinoma	Primary: 
 • No serious adverse events related to CellFX Treatment or Procedure Secondary: 
 • Local Skin Reactions (Investigator) • Procedural pain assessment (Subject)
Effectiveness To evaluate the effectiveness of the CellFX System in adults with low-risk basal cell carcinoma	Primary: 
 • Complete histological clearance of the target lesion on microscopic evaluation of hematoxylin and eosin stains Secondary: 
 • Visible/clinical clearance of the target lesion by clinical/dermatoscopic evaluation • Partial response of the study lesion as assessed by WHO criteria ($\geq 50\%$ decrease in the product of the longest perpendicular diameters of each target lesion) • SCAR-Q Appearance Scale (Subject) • Manchester Scar Scale (Investigator) • Healing assessment questions (Investigator)

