5.2 Risks

For detailed information on the risks of the devices used in the study procedure, including a complete list of warnings, precautions, and potential adverse events, please refer to the Instructions for Use (IFU) for the Pulse Bioscience CellFX® System.

An additional risk for study participants is the delay in performing surgical excision of the tumor; however, basal cell carcinomas are slow-growing, so a delay of 60 days is considered a minimal risk. The wait times for standard surgical excisions are often longer than 60 days in some areas and practices. Because biopsy and surgical excision are standard of care for basal cell carcinoma and will also be occurring in this study, risks of these procedures are not considered in the benefit/risk assessment.

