6.4.1 Primary Safety Endpoint

The primary safety endpoint is the incidence of any serious AEs or complications associated with the application of NPS (procedure and treatment). Information about AEs and complications will be solicited by site investigators at scheduled follow-up visits. The count and proportion with the primary safety endpoint will be calculated along with a 95% confidence interval. Adverse events and complications will also be summarized by MedDRA preferred term.

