8.0 ADVERSE EVENTS

Pulse Biosciences will classify each reported Adverse Event according to ISO 14155:2011. All protocol specific AEs, whether device-related or not, will be recorded on the AE case report form and reported. Data to be collected will include the description of the AE, onset, and resolution dates (or whether the AE is ongoing), severity, management/treatment, outcome, and determination of the relationship to the device and/or procedure. All AEs related to the lesion site(s) should be reported and classified by the site Investigator and be followed by the Investigator to determine the relationship of the AE to the device or the study procedure.

All AE information will be collected from enrollment through the last study visit at 60 days following the surgical excision of the BCC lesion(s) (120 Days after the CellFX treatment session). All AEs will be followed until the event has resolved (in the case of permanent impairment, the event will be followed until it stabilizes, and the overall clinical outcome has been ascertained). Medical occurrences that begin before receiving a CellFX treatment but after obtaining informed consent will be recorded on the Medical History section of the CRF rather than the AE section.

When reporting AEs/SAEs, the Investigator should include the following information:

- Description of event
- Onset of event
- Duration of event (including resolution dates or whether the AE is ongoing)
- Severity
- Relationship to device or procedure
- Action taken
- Subject outcome

Severity describes the intensity of an event and will be assessed as:

- **Mild:** The AE does not interfere in a significant manner with the subject's normal functioning level.
- **Moderate:** The AE produces some impairment of function but not hazardous to health.
- **Severe:** The AE produces significant impairment of function or incapacities and/or it is a hazard to the subject.

Relationship to device or procedure will be assessed as:

- **Unlikely:** There is no indication that the AE was caused by the investigational or standard of care device.
- **Possibly:** It cannot be excluded that the AE was caused by the investigational or standard of care device.
- **Likely:** A causal relationship between the investigational or standard of care device and the AE is at least a reasonable possibility, i.e. there is evidence or argument suggesting a causal relationship.

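### Section 8.0 grades AE relationship in one pooled question, so after the Day 60 excision the stated scale does not separate CellFX from surgery, and no rule links its grades to the CellFX-only safety endpoint

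*Combined protocol and SAP*

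**What the plan says.** **The endpoint.** Table 1 in Section 3.1 gives the primary safety endpoint as "No serious adverse events related to CellFX Treatment or Procedure". Section 6.4.1 describes it as the incidence of "serious AEs or complications associated with the application of NPS (procedure and treatment"), reported as a count and proportion with a 95% confidence interval. Both are limited to the investigational treatment.

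**The attribution scale.** Section 8.0 lists among the AE data a "determination of the relationship to the device and/or procedure", and then defines three grades. The middle one, named Possibly, is worded "It cannot be excluded that the AE was caused by the investigational or standard of care device". The lowest grade (Unlikely) is used where "There is no indication that the AE was caused by the investigational or standard of care device", and the highest grade (Likely) is used where "A causal relationship between the investigational or standard of care device and the AE is at least a reasonable possibility".

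All three put the investigational device and a standard-of-care device into the same question. Neither Section 8.0 nor Section 6.4.1 describes a separate item for each, or says which grades count as related.

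**The design.** Section 3.2 has each treated lesion excised with a margin at the 60-day visit. Section 5.2 describes excision as standard of care. On the collection period, Section 8.0 says "All AE information will be collected from enrollment through the last study visit at 60 days following the surgical excision of the BCC lesion(s"), which is 120 days after the CellFX session.

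**The concern.** Two interventions are applied in sequence to the same skin, and the primary safety endpoint concerns only the first. A single-arm study has no control group to show what excision alone would produce, so the investigator's causality judgement is the main means of telling the two apart. The only causality scale in the protocol does not ask for that distinction.

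The error can go in either direction. If a site takes the pooled wording to cover the excision, a surgical complication may be graded Possibly or Likely and then be counted against CellFX. Conversely, a late CellFX effect, such as poor healing of treated skin, may later be put down to surgery, with no CellFX-specific grade under this scale to set against that.

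What is at stake is the primary safety count, the sorting of non-serious events into device effects and other AEs, and the safety information that Section 1.6 intends to carry into a pivotal study.

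**Working it through.** The plan states no power, event rate or precision target for safety, and the maximum of 30 subjects (Section 6.5) has no formula behind it. There is no planned figure to reproduce. The check is a comparison of the sections, followed by an illustration of scale.

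**1. Which events are affected?** The AE window runs from Day 0 to Day 120: 60 days before the excision plus 60 after it gives 120, matching Section 8.0. The post-excision share is 60/120 = 50%. This is a share of time and does not measure bias. Section 8.0 records onset dates, and an event that began before the excision cannot have been caused by it. The ambiguity is therefore confined to events with onset from the excision to Day 120.

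**2. Does the scale supply what the endpoint needs?**

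| Element | Refers to |
|---|---|
| Primary safety endpoint (Table 1, 6.4.1) | CellFX/NPS only |
| ADE and SADE (8.1.2, 8.1.4) | Investigational device only |
| Relationship grades (8.0) | Investigational or standard-of-care device, pooled |
| Rule from grade to endpoint | None stated |

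The endpoint and the device-effect definitions name the right target, but the scale does not measure it. A Possibly or Likely grade on a post-excision event does not by itself say which intervention is suspected, and the plan does not say whether Possibly counts.

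**3. How much could one event move the result?** This is an illustration only, with N = 30 and exact (Clopper-Pearson) 95% intervals. For x = 0 the upper limit is 1 − 0.025^(1/30) = 11.6%. For x > 0 the limits are the 2.5% point of Beta(x, 30 − x + 1) and the 97.5% point of Beta(x + 1, 30 − x).

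| Serious events counted as related | Proportion | Exact 95% CI |
|---|---|---|
| 0/30 | 0% | 0 to 11.6% |
| 1/30 | 3.3% | 0.1 to 17.2% |
| 2/30 | 6.7% | 0.8 to 22.1% |

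**4. How likely is such an event?** The documents give no rate of serious excision-caused events. With an assumed per-subject rate p, the chance of at least one in 30 subjects is 1 − (1 − p)^30:

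- p = 1%: 1 − 0.99^30 = 26%
- p = 2%: 1 − 0.98^30 = 45%
- p = 5%: 1 − 0.95^30 = 79%

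These are chances that an event occurs. They are not chances that it is misattributed.

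**The case against.** A reader might infer that the CellFX safety endpoint cannot be isolated at all. The documents do not support that. The endpoint and the ADE and SADE definitions are tied to the investigational treatment, the sponsor classifies each AE under ISO 14155, onset dates clear every pre-excision event of excision as a cause, and the few serious events could be reviewed individually. This limits the point to post-excision events. It does not close the gap there, because an onset date after the excision does not tell a surgical complication from a CellFX effect.

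A reader might also infer that sites are obliged to grade excision complications as related. That goes too far. The grades speak of a standard-of-care device; excision is a procedure, and no such device is identified. The term is undefined, so sites may read it differently, and that also calls for clarification.

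Other points on this side stand:

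- The case report forms are a separate attachment (Appendix B) and were not available. They may already hold separate attribution fields.
- A post-excision bleed, infection or wound opening counts as a serious AE only if it meets Section 8.1.3. Eligible lesions are at most 1.5 cm, suitable for linear excision and away from the excluded sites.
- Section 6.4.1 plans AE summaries by MedDRA preferred term. No table of related AEs is specified, so none can be said to be distorted.
- In Table 6, SAEs and SADEs share the same 3-calendar-day limit for sites. Attribution changes site timing only for non-serious events, although it also bears on the sponsor's own evaluation report.
- The statement in Section 5.2 that "risks of these procedures are not considered in the benefit/risk assessment" concerns the prospective weighing of risk, not causality grading, and adds nothing here.

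The argument that miscounting could only overstate CellFX harm does not stand, since late CellFX effects could equally be put down to surgery.

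**Conclusion.** The concern holds for AEs with onset from the excision to Day 120. For these, the stated scale does not separate CellFX from excision, and no rule turns its grades into the CellFX-only primary endpoint. Events before the excision are unaffected, and if no serious event follows the excision this ambiguity leaves the primary safety rate unchanged.

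The size is not known. One or two misattributed serious events among 30 would be the difference between 0% and 3.3% or 6.7%, with the intervals shown above; these figures rest on assumed events and on the maximum enrolment. The direction is also open, so a claim of upward bias would go beyond the documents.

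The conclusion assumes that the case report forms follow the wording of Section 8.0. If they already separate the two sources, what remains is to align the protocol text and add the mapping rule. The study is descriptive, with no hypothesis tests and no interim analysis, so this is a should-fix rather than a must-fix. It is best settled before enrolment, because causality judgements not recorded at the time are hard to recover.

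**What to change.** 1. In Section 8.0, and on the AE form if it does not already do so, replace the pooled question with two items on the same three grades: (a) relationship to the CellFX device or CellFX procedure, and (b) relationship to the Visit 6 excision. Remove or define the term for the standard-of-care device.
2. In Section 6.4.1, state that only item (a) graded Possibly or Likely feeds the primary safety endpoint.
3. Tabulate AEs by onset before or after the excision. Use each subject's actual excision date rather than Day 60, because Table 3 allows a window of ±5 days.

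The cost is protocol wording, at most one more form field, and one table split. There are no extra visits and no change to sample size. The small downside is that some events after the excision will be graded possibly related to both. Those events would still count under item (a), and the table would show openly that their attribution is shared.

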8.1 Adverse Event Definitions

8.1.1 Adverse Event (AE): (*ISO 14155:2011 3.2*)

Any untoward medical occurrence, unintended disease or injury, or untoward clinical signs (including abnormal laboratory findings) in subjects, users, or other persons, whether or not related to the investigational medical device.

NOTE 1: This definition includes events related to the investigational medical device.

NOTE 2: This definition includes events related to the procedures involved.

***For the purposes of this protocol, only dermatologic AEs will be reported to the Sponsor.**

8.1.2 Adverse Device Effect (ADE): (*ISO 14155:2011 3.1*)

Adverse event related to the use of an investigational medical device

NOTE 1: This definition includes adverse events resulting from insufficient or inadequate instructions for use, deployment, implantation, installation, or operation, or any malfunction of the investigational medical device.

NOTE 2: This definition includes any event resulting from use error or from intentional misuse of the investigational medical device

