1.5 Alternative Approach

CellFX® System

The CellFX System is intended to be used for dermatological procedures in adult patients (greater than or equal to 22 years old) for the reduction, removal, and/or clearance of cellular-based benign lesions and low-risk basal cell carcinoma (BCC), as an alternative to surgery and other more destructive methods for removing skin lesions. The CellFX System utilizes localized delivery of a timed series of low energy, nanosecond electrical pulses that can trigger regulated cell death. The effect on tissue takes place in a very shallow depth of skin directly below the sterile treatment tip. Histology of skin treated with CellFX has demonstrated selective effects on cellular structures, including melanocytes, epidermal cells, and adnexal structures, including sebaceous glands and eccrine glands, with no apparent damage to the adjacent acellular dermis. The device delivers less energy to tissue, and does not emit thermal energy like laser, electro-surgery, or electro-cautery equipment.

Prior Clinical Studies Summary

Thirteen (13) clinical studies have been or are currently being conducted using IRB approved non-significant risk protocols and consent with the Nano-Pulse Stimulation (NPS) device. Two approved IDE pivotal studies are currently being conducted. A combined total of approximately 3,600 NPS application cycles have been delivered to about 700 adult Subjects. Anatomic locations where NPS has been used include the face, trunk, neck, arms, legs, hands, and feet. Discomfort in all protocols was managed with localized injected buffered Lidocaine, often with epinephrine. Side effects consisted of relatively minor reactions consistent with routine wound healing. No device or procedure complications and no serious related adverse events were reported. Only minor expected adverse skin effects were observed that are expected to resolve.

A Non-Significant Risk (NSR) Acne Feasibility study (NP-AF-009) was conducted using the Nano-Pulse Stimulation (NPS) device on back acne. The study involved the treatment of acne lesions in a 7cmx7cm area of the back with 49 cycles of energy delivered via the 10.0mm x 10.0mm treatment tip across a range of energy settings. The entire treatment area healed as expected with some residual hyperpigmentation, which is expected to resolve over time.

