8.3 Safety Reporting Requirements

Table 6 summarizes the time sensitive requirements for adverse events and device deficiencies. The Sponsor is the contact person for these reporting requirements.

Table 6. Investigator Responsibilities for Submitting Adverse Events to the Sponsor

Type of Adverse Event	Reporting Timeframe
*Serious Adverse Device Effects (SADE), including Unanticipated Serious Adverse Device Effect (USADE)	As soon as possible, but in no case later than 3 calendar days after the clinical site first learns of the event or of new information in relation with an already reported event
**Serious Adverse Events (SAE)	As soon as possible, but in no case later than 3 calendar days after the clinical site first learns of the event or of new information in relation with an already reported event
Adverse Device Effects (ADE)	As soon as possible, but in no case later than 3 calendar days after the clinical site study team first learns of the event or of new information in relation with an already reported event
All other AEs (dermatologic only)	Submit in a timely manner after the clinical site first learns of the event
**Device Deficiency with SADE potential	As soon as possible, but in no case later than 3 calendar days after the clinical site study team first learns of the deficiency or of new information in relation with an already reported deficiency
All other Device Deficiencies	Submit in a timely manner after the clinical site first learns of the deficiency

*The Sponsor will report the results of an evaluation of an unanticipated serious or serious adverse device effect to the FDA and all reviewing IRBs and investigators within 10 working days after the Sponsor first received notice of the adverse effect per 21 CFR 812.150.

**It is the responsibility of the investigator to inform their IRB of serious adverse events and device deficiencies as required by their IRB guidelines.

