9.5.2 Periodic Monitoring Visits (Onsite and Remote)

Periodic monitoring visits will be made at the investigational site throughout enrollment of the clinical study to assure that the Investigator obligations are fulfilled, and all applicable regulations and guidelines are being followed. These visits will assure that the facilities are still acceptable; the protocol and investigational plan are being followed, the IRB/HREC has been notified of approved protocol changes as required, complete records are being maintained, appropriate and timely reports have been made to the Sponsor and the IRB, device and device inventory are controlled and the Investigator is carrying out all agreed activities. The monitor will verify accuracy of CRF or EDC completion against source documents maintained at the site.

During monitoring visits, the Monitor will perform a review of study eligibility, Inclusion/Exclusion criteria, informed consent, all reports of device malfunction, all events meeting criteria for serious adverse event reporting as well as safety and efficacy endpoints.

Additional review will be performed on a site-by-site basis, as warranted by the findings of previous monitoring visits.

The monitor will ensure that Investigators are aware of the regulatory requirement to maintain information in the study subject's medical records which corroborate data collected on the CRF or EDC system. To comply with these regulatory requirements, the following information will be maintained and made available as required by the sponsor and/or regulatory inspectors:

The monitor will compare key variables (demographics, inclusion/exclusion criteria, and safety) on the CRFs or EDC database with each subject's source documents. Any discrepancies will be noted and resolved.

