10.2 Data Collection and Reporting

Case report forms or source documents will be used to record demographic, procedural, and follow-up data, as well as any adverse events which may occur during the study period. The AEs and incidence of morbidity and mortality will be reviewed with Investigators to assess the safety of the device and the procedure.

The Investigator must comply with the safety reporting requirements specified in **Section 8.3**.

Qualified study staff at each clinical site will perform primary data collection drawn from source-

document (hospital or clinic chart) reviews. The Monitor will perform clinical monitoring, including review of CRFs, source documents and/or Electronic Data Capture (EDC) system with verification of study eligibility, informed consent process, scheduled follow-up visits and AEs to the source documentation.

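### The note under 8.1.1 limits Sponsor reporting to dermatologic AEs without exception, while Table 6 requires SADEs, SAEs and ADEs of any kind within 3 calendar days; the note should be brought into line with Table 6

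*Combined protocol and SAP*

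**What the plan says.** Section 8.1.1 gives the general definition of an adverse event and ends with a starred note: "For the purposes of this protocol, only dermatologic AEs will be reported to the Sponsor". The note makes no exception for serious or device-related events.

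The subsections that follow build on that definition. An ADE (8.1.2) is an adverse event related to use of the device, an SAE (8.1.3) is an adverse event with one of the listed serious outcomes, and a SADE (8.1.4) is an ADE with such an outcome.

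Table 6 in section 8.3 sets the investigator's reporting duties to the Sponsor. SADEs, SAEs and ADEs each have a limit of 3 calendar days and no restriction by body system. A dermatologic restriction appears on one row only: "All other AEs (dermatologic only". Section 10.2 makes the table binding: "The Investigator must comply with the safety reporting requirements specified in" Section 8.3.

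The primary safety endpoint has no dermatologic limit in either place where it is stated. Section 6.4.1 says "The primary safety endpoint is the incidence of any serious AEs or complications associated with the application of NPS (procedure and treatment", and Table 1 in section 3.1 says "No serious adverse events related to CellFX Treatment or Procedure".

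**The concern.** The protocol contains two reporting rules that give different answers for the same event. Take a serious, non-dermatologic event that the investigator considers related to the CellFX procedure. Table 6 requires it to reach the Sponsor within 3 calendar days. The note, read as written, says it is not reported at all. No sentence says which rule prevails.

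Such an event counts toward the primary safety endpoint. A non-serious, non-dermatologic ADE is not part of the serious-event count, but it belongs in the summary of adverse events by preferred term in section 6.4.1. Under the literal note, either could be missing from the Sponsor's data or arrive late. Timing matters separately: the footnote to Table 6 starts the Sponsor's 10-working-day reporting duty to the FDA, the IRBs and the investigators when the Sponsor first receives notice, so an event that is held back does not start that clock. Section 1.6 says the data will be used to design a pivotal study.

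**Working it through.** The finding rests on the text. The plan states no figure to reproduce: there is no hypothesis test, and 30 is a cap on enrolment, not the result of a calculation (section 6.5).

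**The two rules side by side**

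| Non-dermatologic event | Note in 8.1.1, read literally | Table 6 in 8.3 |
|---|---|---|
| SADE | not reported | within 3 calendar days |
| SAE, not device-related | not reported | within 3 calendar days |
| ADE, not serious | not reported | within 3 calendar days |
| Any other AE | not reported | not reported (row limited to dermatologic events) |

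1. By the definitions in 8.1.2 to 8.1.4, every ADE, SAE and SADE is an AE. A rule about which AEs are reported therefore covers them unless it says otherwise, and the note does not.
2. The rules agree on the last row and disagree on the first three.
3. The primary safety endpoint draws on serious related events of any body system, so it depends on rows where the rules disagree.
4. Section 8.0 does not settle the matter. It calls for recording and reporting of protocol-specific AEs but does not define that term.

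**What one event does to the result (illustration only)**

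Inputs: n = 30, the maximum number treated (section 6.5); a proportion with a 95% confidence interval (section 6.4.1). The plan does not name the interval method, so the exact Clopper-Pearson interval is assumed.

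- 0 events: estimate 0/30 = 0%. The lower limit is 0. The upper limit is 1 − 0.025^(1/30) = 11.6%.
- 1 event: estimate 1/30 = 3.3%. The lower limit is 1 − 0.975^(1/30) = 0.08%, or 0.1% rounded. The upper limit solves (1 − p)^30 + 30p(1 − p)^29 = 0.025, which gives p = 17.2%.

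One unreported event would thus change the reported result from 1/30 (0.1 to 17.2%) to 0/30 (0 to 11.6%), which makes the device look safer than it was. If every site follows Table 6, the undercount of serious events from this cause is zero.

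**The case against.** The best reply is that the documents already contain the reconciling reading. Table 6 repeats the dermatologic limit and places it on the residual row, which makes sense only if the rows above it are not limited. Table 6 is the operative reporting section and section 10.2 makes it mandatory. The note stands under the general definition, ahead of the subsections on device effects and serious events, and can be read as shorthand for the residual row. Section 10.2 also plans a broad review, "The AEs and incidence of morbidity and mortality will be reviewed with Investigators to assess the safety of the device and the procedure", which fits the Table 6 reading and is not a further conflict. All of this stands, and it makes Table 6 the probable intention. It does not remove the literal wording of the note, which says only and gives no cross-reference.

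The second reply is that there are backstops. Section 10.2 has any adverse event during the study recorded on case report forms or in source documents. Under section 9.5.2 the monitor reviews "all events meeting criteria for serious adverse event reporting as well as safety and efficacy endpoints". The primary safety result is an end-of-study count with no interim analysis (section 6.8), so an event found late can still enter it. This also stands in part. These routes can recover an event recorded at the site, but a monitoring visit does not secure a 3-day report.

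A reader might infer that serious events will be lost, or that the primary safety endpoint is in effect confined to skin. The documents do not support either: the endpoint is worded without that limit, and compliance with Table 6 loses no serious event. A reader might also try to put a probability on the problem from section 1.5, which says of earlier studies that "No device or procedure complications and no serious related adverse events were reported". That does not bound the rate here. The earlier studies covered other lesion types, some were still running, and the section does not say how non-dermatologic events were collected.

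**Conclusion.** The concern holds as an inconsistency between two reporting instructions, one of which, followed literally, would withhold events that belong in the primary safety count and in the AE summary. Confidence in the mismatch is high because it can be read directly from 8.1.1 to 8.1.4 and Table 6. The practical effect is conditional: none for serious events if sites follow Table 6, and a missing or late report if a site follows the note and such an event occurs. The documents give no basis for estimating how often that would happen. The comparison of 0/30 with 1/30 shows only what a single event is worth, assuming full enrolment and an exact interval. The point should be fixed because it touches a primary endpoint and the remedy is simple, but it is not evidence that the safety analysis is unsound.

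**What to change.** Amend the note under 8.1.1 to read: *All SAEs, SADEs and ADEs are reported per Table 6 regardless of body system; the dermatologic-only limit applies only to the 'All other AEs' row of Table 6.*

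The cost is one sentence of protocol wording. It adds no reporting burden beyond the present plan, because Table 6 already requires these reports, and it changes no endpoint, analysis or sample size.
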